t) will be extrapolated to infinity using $λ_z$ to obtain AUC. The area under the concentrationtime curve across the dosing interval, AUC_{ss} will be calculated using the linear trapezoidal rule. The apparent clearance (CL/F following the single dose and CL_{ss}/F following multiple dosing) will be determined from the ratio of dose/AUC or dose/AUC_{ss}. The volume of distribution (V_{ss}/F or V_z/F) will be determined from the mean residence time (MRT) x CL/F and/or the accumulation ratio (R_{AC}) will be calculated as the ratio of the AUC₍₀₋₂₄₎ on Day 15 and Day 1. The time dependency of the pharmacokinetics on multiple dosing will be assessed by the calculation of the ratio of AUC₍₀₋₂₄₎ Day 15/AUC Day 1.

Where possible the appropriate pharmacokinetic parameters will also be determined for the metabolites of AZD9291.

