Plasma concentrations of AZD9291, AZ5104 and AZ7550 will be summarised by nominal sample time. Plasma concentrations and derived PK parameters will be summarised by dose level. Parameters following single and multiple dosing will be summarised separately. Plasma concentrations at each time point will be summarised according to dose by the following summary statistics:

- The geometric mean (gmean, calculated as $\exp [\mu]$, where μ is the mean of the data on a logarithmic scale)
- Coefficient of variation (CV, calculated as $100 \sqrt{[exp(s^2)-1]}$, where s is the standard deviation of the data on a log scale)
- Gmean \pm standard deviation (calculated as exp[$\mu \pm s$])
- Arithmetic mean calculated using untransformed data
- Standard Deviation calculated using untransformed data
- Minimum
- Maximum
- Number of observations

The following summary statistics will be presented for AUC, AUC₍₀₋₂₄₎, AUC_(0-t), AUC_{ss}, C_{max} , $C_{ss max}$ and $C_{ss min}$:

- Gmean, calculated as $exp[\mu]$, where μ is the mean of the data on a logarithmic scale)
- CV, calculated as $100 \sqrt{[\exp(s^2)-1]}$, where s is the standard deviation of the data on a log scale)
- Arithmetic mean calculated using untransformed data
- Standard deviation calculated using untransformed data
- Minimum
- Maximum
- Number of observations

The following summary statistics will be presented for CL/F, CL_{ss}/F, volume of distribution, $t_{1/2\lambda z}$, R_{AC} , time dependency:

Revised Clinical Study Protocol Drug Substance AZD9291 Study Code D5160C00001 Edition Number 3 Date

- Arithmetic mean
- Standard deviation
- Minimum
- Maximum
- Number of observation

The following summary statistics will be presented for t_{max} and t_{max ss}:

- Median
- Minimum
- Maximum
- Number of observations

The pharmacokinetic data for AZD9291, AZ5104 and AZ7550 after a single-dose and separately, at steady state will also be displayed graphically. Displays will include plasma concentration patient profiles (on the linear and log-scale) versus time and gmean concentration (+/-standard deviation) versus time, stratified by dose.

Scatter plots of PK parameters versus dose, or log-dose will also be considered following both single and multiple dose administration of AZD9291 to assess dose proportionality.

In a preliminary assessment of dose proportionality, log-transformed AUC and C_{max} parameter estimates will be examined using the Power Model:

parameter = $e^a (dose)^b$

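### Apparent clearance, R_AC and the time-dependency ratio get arithmetic summaries only, although each is a quotient of AUCs that are summarised and modelled on the log scale (minor; free improvement)

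*Protocol*

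**What the plan says.** Section 7.9 (Pharmacokinetics) sets out separate lists of summary statistics.

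- **AUC, AUC(0-24), AUC(0-t), AUCss, Cmax, Css max and Css min.** These get a geometric mean and a CV of 100√[exp(s²)−1], "where s is the standard deviation of the data on a log scale". They also get "Arithmetic mean calculated using untransformed data", SD, minimum, maximum and number.
- **The derived parameters.** The text reads "The following summary statistics will be presented for CL/F, CL_{ss}/F, volume of distribution", and continues with terminal half-life, R_AC and time dependency. The statistics are arithmetic mean, SD, minimum, maximum and number of observations. There is no geometric mean, log-scale CV, median or interval.

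Section 7.4 defines apparent clearance per patient as dose over AUC (single dose) or dose over AUCss (multiple dose). R_AC "will be calculated as the ratio of the" AUC(0-24) values on Day 15 and Day 1. For the other ratio, "The time dependency of the pharmacokinetics on multiple dosing will be assessed by the calculation of the ratio of" AUC(0-24) on Day 15 to AUC on Day 1.

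For dose proportionality, Section 7.9 says that "log-transformed AUC and C_{max} parameter estimates will be examined using the Power Model". If proportionality fails, log dose-normalised AUC is modelled and back-transformed with 90% confidence intervals.

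**The concern.** The protocol uses two scales for the same information. Single-dose dose-normalised AUC is the reciprocal of CL/F, so it is analysed on the log scale in one paragraph and its reciprocal is summarised arithmetically in another. This has two consequences.

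1. A time-dependency ratio is read against 1. The arithmetic mean of a right-skewed ratio centred geometrically on 1 tends to sit above 1. It also depends on which way up the ratio is written, so it can suggest falling clearance in one direction and rising clearance in the other.
2. A reader who divides dose by the tabulated mean AUC will not recover the tabulated mean CL/F.

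Single-dose and steady-state pharmacokinetics are a secondary objective (Section 1.2). What is at stake is how clearly that objective is reported. Patient safety and the primary endpoints are not affected.

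**Working it through.** **Inputs.** The definitions come from Section 7.4, and the summary lists and CV formula from Section 7.9. In Table 5 (Section 6.6.1) the Cycle 0 single-dose profile is for dose escalation only; on Cycle 1 Day 1 there is a pre-dose sample only. Both ratios need a Day 1 AUC, so they exist only for escalation patients, in cohorts of 3 to 6 evaluable patients (Section 7.2.1). The protocol states no CV and no figure of its own on this point, so there is nothing to reproduce. The CV is an assumption, taken over a range. For the two ratios it must be the CV of the within-patient ratio, since each patient serves as his or her own control.

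**1. Time-dependency ratio, no time dependency, geometric mean 1.** From the protocol's CV formula, s² = ln(1+CV²). For a log-normal ratio, E[arithmetic mean] = exp(s²/2) = √(1+CV²). The sampling SD of the mean of n ratios is CV·√(1+CV²)/√n.

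| Assumed CV | Expected arithmetic mean | Shift above 1 | SD of mean, n = 6 | Share of n = 6 cohorts with mean above 1 |
|---|---|---|---|---|
| 20% | √1.04 = 1.02 | 0.02 | 0.08 | 58% |
| 30% | √1.09 = 1.04 | 0.04 | 0.13 | 62% |
| 50% | √1.25 = 1.12 | 0.12 | 0.23 | 68% |

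The shares come from simulation. For the geometric mean the share is 50% at every CV and n.

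**2. Chance of a reported mean above 1.10 at n = 6 with no time dependency.** The 1.10 mark is only a yardstick; the protocol sets no threshold. For the geometric mean the chance is 1 − Φ(ln 1.10 ÷ (s/√6)). At CV 50%, s = 0.472, so z = 0.0953 ÷ 0.193 = 0.49 and the chance is 31%. For the arithmetic mean, simulation gives 49%. The corresponding pairs (arithmetic, geometric) are 31% and 21% at CV 30%, and 17% and 12% at CV 20%.

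**3. Dependence on direction.** Take two patients with ratios 0.5 and 2.0. The arithmetic mean is (0.5 + 2.0)/2 = 1.25. Inverted, the ratios are 2.0 and 0.5, and the mean is again 1.25. The geometric mean is √(0.5 × 2.0) = 1.00 both ways.

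**4. R_AC.** The same factor √(1+CV²) applies to its expected arithmetic mean relative to its geometric mean. Its reference value is not 1, because a drug that accumulates has R_AC above 1 under linear kinetics.

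**5. CL/F against AUC.** For the same patients, the inequality of harmonic, geometric and arithmetic means gives

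mean(dose/AUC) ≥ dose/geometric mean AUC ≥ dose/arithmetic mean AUC,

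with equality only if all AUCs are equal. No distribution is assumed. If AUC is log-normal, the large-sample ratio of mean CL/F to dose over geometric mean AUC is √(1+CV²). Against dose over arithmetic mean AUC it is 1+CV². Here the CV is the between-patient CV of AUC.

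| Assumed CV of AUC | vs dose/geometric mean AUC | vs dose/arithmetic mean AUC |
|---|---|---|
| 30% | 1.04 (n = 6: 1.04) | 1.09 (n = 6: 1.08) |
| 50% | 1.12 (n = 6: 1.10) | 1.25 (n = 6: 1.21) |
| 70% | 1.22 (n = 6: 1.18) | 1.49 (n = 6: 1.41) |

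The n = 6 values are simulated. The arithmetic mean AUC that Section 7.9 also lists therefore widens the gap. Geometric mean CL/F equals dose over geometric mean AUC exactly.

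**The case against.** The strongest case on the other side is that these are descriptive rows in a table. No test, threshold or decision rule is attached to CL/F, R_AC or time dependency. The maximum tolerated dose rests on dose-limiting toxicities, and the formal dose-proportionality work is already on the log scale. An arithmetic mean of per-patient clearances is a legitimate summary, and the protocol nowhere claims that it reconciles with dose over mean AUC. The list does not bar further statistics. All of this stands, and it is why the point is minor. It does not remove the point: the protocol names the statistics that will be presented, so this is a stated choice, and it differs from the scale used for the AUCs.

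Some stronger readings are tempting but unsupported.

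- **That the plan would declare time dependency where there is none.** The upward reading is a tendency. In cohorts of six, about 32% to 42% of arithmetic means would not exceed 1 at CVs of 50% to 20%. The shift is below sampling error, and a geometric mean from so few patients is imprecise too.
- **That the distortion grows clear in cohorts of about 30.** Expansion and extension patients have no single-dose profile in Table 5, so neither ratio can be formed for them.
- **That an R_AC above 1 is an artefact.** R_AC has no null value of 1.
- **That this ratio is the only tool for changing clearance, with no measure of spread.** Section 7.5.1 plans population pharmacokinetics, CL/F and CLss/F are both reported, and SD and number are listed. What is missing is an interval on the appropriate scale.

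Separately, Table 5 has no full profile on Cycle 1 Day 15, the day named in both ratios; the full steady-state profile is on Cycle 2 Day 1. That is a different issue, and the present point holds whichever day is used.

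**Conclusion.** The point holds as a minor reporting inconsistency. The mismatch between mean CL/F and dose over mean AUC is certain in any sample with unequal AUCs. Its size, and the upward shift in the two ratios, depend on CVs that the protocol does not give. For the ratios the expected inflation is about 2%, 4% and 12% at assumed within-patient ratio CVs of 20%, 30% and 50%, if log-normal. It applies to escalation cohorts of 3 to 6 per dose, where it is smaller than sampling error. The largest practical contrast in that CV range is at CV 50% and n = 6: a 49% chance of a mean above 1.10 with no time dependency, against 31% for the geometric mean. No dose decision or primary conclusion rests on this, so it is a free improvement and not a design error.

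**What to change.** In Section 7.9, add the geometric mean and log-scale CV, as already defined there for AUC, to the list for CL/F, CLss/F and volume of distribution. Report R_AC and time dependency as geometric mean ratios with 90% confidence intervals, obtained from the within-patient differences in log AUC and back-transformed. Keep the arithmetic rows for those who want them. In cohorts of 3 to 6 the intervals will be wide, which tells the reader how little each cohort says on its own.

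The cost is a sentence or two in Section 7.9 and a few extra rows in the PK tables. No new samples, visits or patients are needed.

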8.2 Overdose

There are no data on overdosing since this is the first study in humans with AZD9291. There is no definition of what constitutes an overdose. There is no known antidote. Investigators will be advised that any patient who receives a higher dose than that intended should be monitored closely, managed with appropriate supportive care and followed up expectantly.

Such overdoses should be recorded as follows:

- An overdose with associated AEs/SAEs is recorded as the AE diagnosis/symptoms on the relevant AE/SAE modules in the CRF and on the overdose CRF module.
- An overdose with no associated symptoms is only reported on the overdose CRF module.

If an overdose occurs in the course of the study, then investigators or other site personnel inform appropriate AstraZeneca representatives immediately, or **no later than 24 hours** of when he or she becomes aware of it.

Revised Clinical Study Protocol Drug Substance AZD9291 Study Code D5160C00001 Edition Number 3 Date

The designated AstraZeneca representative works with the investigator to ensure that all relevant information is provided to the AstraZeneca Patient Safety data entry site.

For overdoses associated with a SAE, standard reporting timelines apply, see Section 6.4.4. For other overdoses, reporting should be done within 28 days.

8.3 Pregnancy

All pregnancies and their subsequent outcome (spontaneous miscarriage, elective termination, ectopic pregnancy, normal birth or congenital abnormality) should be reported to AstraZeneca using the appropriate forms.

8.3.1 Maternal exposure

If a patient becomes pregnant during the course of the study investigational product should be discontinued immediately.

Pregnancy itself is not regarded as an adverse event unless there is a suspicion that the investigational product under study may have interfered with the effectiveness of a contraceptive medication. Congenital abnormalities/birth defects and spontaneous miscarriages should be reported and handled as SAEs. Elective abortions without complications should not be handled as AEs. The outcome of a pregnancy should be followed up and documented even if the patient was withdrawn from the study.

If a pregnancy occurs during exposure to investigational product or in the 28 days after discontinuing investigational product, then investigators or other site personnel inform appropriate AstraZeneca representatives immediately, or **no later than 24 hours** of when he or she becomes aware of it.

The designated AstraZeneca representative works with the investigator to ensure that all relevant information is provided to the AstraZeneca Patient Safety data entry site within 1 or 5 days for SAEs, (see Section 6.4.4) and within 28 days for all other pregnancies.

The same timelines apply when outcome information is available.

Appendix B Additional Safety Information

FURTHER GUIDANCE ON THE DEFINITION OF A SERIOUS ADVERSE EVENT (SAE)

Life threatening

'Life-threatening' means that the patient was at immediate risk of death from the adverse event (AE) as it occurred or it is suspected that use or continued use of the product would result in the patient's death. 'Life-threatening' does not mean that had an AE occurred in a more severe form it might have caused death (eg, hepatitis that resolved without hepatic failure).

Hospitalisation

Out-patient treatment in an emergency room is not in itself a serious AE, although the reasons for it may be (eg, bronchospasm, laryngeal oedema). Hospital admissions and/or surgical operations planned before or during a study are not considered AEs if the illness or disease existed before the patient was enrolled in the study, provided that it did not deteriorate in an unexpected way during the study.

Important medical event or medical intervention

Medical and scientific judgement should be exercised in deciding whether a case is serious in situations where important medical events may not be immediately life-threatening or result in death, hospitalisation, disability or incapacity but may jeopardise the patient or may require medical intervention to prevent one or more outcomes listed in the definition of serious. These should usually be considered as serious.

Simply stopping the suspect drug does not mean that it is an important medical event; medical judgement should be used.

Examples of such events are:

- Angioedema not severe enough to require intubation but requiring iv hydrocortisone treatment
- Hepatotoxicity caused by paracetamol (acetaminophen) overdose requiring treatment with N-acetylcysteine
- Intensive treatment in an emergency room or at home for allergic bronchospasm
- Blood dyscrasias (eg, neutropenia or anaemia requiring blood transfusion, etc) or convulsions that do not result in hospitalisation
- Development of drug dependency or drug abuse.

A GUIDE TO INTERPRETING THE CAUSALITY QUESTION

The following factors should be considered when deciding if there is a "reasonable possibility" that an AE may have been caused by the drug.

- Time Course. Exposure to suspect drug. Has the patient actually received the suspect drug? Did the AE occur in a reasonable temporal relationship to the administration of the suspect drug?
- Consistency with known drug profile. Was the AE consistent with the previous knowledge of the suspect drug (pharmacology and toxicology) or drugs of the same pharmacological class? Or could the AE be anticipated from its pharmacological properties?
- Dechallenge experience. Did the AE resolve or improve on stopping or reducing the dose of the suspect drug?
- No alternative cause. The AE cannot be reasonably explained by another aetiology such as the underlying disease, other drugs, other host or environmental factors.
- Rechallenge experience. Did the AE reoccur if the suspected drug was reintroduced after having been stopped? AstraZeneca would not normally recommend or support a rechallenge.
- Laboratory tests. A specific laboratory investigation (if performed) has confirmed the relationship?

A "reasonable possibility" could be considered to exist for an AE where one or more of these factors exist.

In contrast, there would not be a "reasonable possibility" of causality if none of the above criteria apply or where there is evidence of exposure and a reasonable time course but any dechallenge (if performed) is negative or ambiguous or there is another more likely cause of the AE.

In difficult cases, other factors could be considered such as:

- Is this a recognised feature of overdose of the drug?
- Is there a known mechanism?

Ambiguous cases should be considered as being a "reasonable possibility" of a causal relationship unless further evidence becomes available to refute this. Causal relationship in cases where the disease under study has deteriorated due to lack of effect should be classified as no reasonable possibility.

Clinical Study Protocol Appendix C		
Drug Substance	AZD9291	
Study Code	D5160C00001	
Edition Number	3	
Date		

Appendix C International Airline Transportation Association (IATA) 6.2 Guidance Document

LABELLING AND SHIPMENT OF BIOHAZARD SAMPLES

International Airline Transportation Association (IATA) classifies biohazardous agents into 3 categories (http://www.iata.org/whatwedo/cargo/dgr/Documents/DGR52_InfectiousSubstances(DGR362).pdf). For transport purposes the classification of infectious substances according to risk groups was removed from the Dangerous Goods Regulations (DGR) in the 46th edition (2005). Infectious substances are now classified either as Category A, Category B or Exempt. There is no direct relationship between Risk Groups and categories A and B.

Category A Infectious Substances are infectious substances in a form that, when exposure to it occurs, is capable of causing permanent disability, life-threatening or fatal disease in otherwise healthy humans or animals. Category A pathogens are eg. Ebola, Lassa fever virus

• are to be packed and shipped in accordance with IATA Instruction 602

Category B Infectious Substances are infectious Substances that do not meet the criteria for inclusion in Category A. Category B pathogens are eg. Hepatitis A, B, C, D, and E viruses, Human immunodeficiency virus (HIV) types 1 and 2. They are assigned the following UN number and proper shipping name:

- UN 3373 Biological Substance, Category B
- are to be packed in accordance with UN3373 and IATA 650

Exempt - all other materials with minimal risk of containing pathogens

- Clinical trial samples will fall into Category B or exempt under IATA regulations.
- Clinical trial samples will routinely be packed and transported at ambient temperature in IATA 650 compliant packaging
- http://www.iata.org/whatwedo/cargo/dgr/Documents/DGR52_PI650_EN.pdf
- Biological samples transported in dry ice require additional dangerous goods specification for the dry-ice content.
- IATA compliant courier and packaging materials should be used for packing and transportation and packing should be done by an IATA certified person, as applicable.
- Samples routinely transported by road or rail are subject to local regulations which require that they are also packed and transported in a safe and appropriate way to contain any risk of infection or contamination by using approved couriers and packaging / containment materials at all times. The IATA 650 biological sample containment standards are encouraged wherever possible when road or rail transport is used.

Appendix D Ethical and Regulatory Requirements

1. ETHICAL AND REGULATORY REQUIREMENTS

1.1 Ethical conduct of the study

The study will be performed in accordance with ethical principles that have their origin in the Declaration of Helsinki and are consistent with the International Conference on Harmonisation (ICH)/Good Clinical Practice (GCP) guidelines, applicable regulatory requirements and the AstraZeneca policy on Bioethics and Human Biological Samples.

The applicable regulatory requirements in Japan are 'Good Clinical Practice for Trials on Drugs (MHLW Ordinance No. 28, 27 March 1997, partially revised by MHLW Ordinance and their related notifications.

1.2 Ethics and regulatory review

An Ethics Committee should approve the final Clinical Study Protocol, including the final version of the Informed Consent Form and any other written information and/or materials to be provided to the patients. This will include approval of the exploratory biomarker and pharmacogenetic research and associated consents forms. The investigator/ The Head of the study site will ensure the distribution of these documents to the applicable Ethics Committee, and to the study site staff.

The opinion of the Ethics Committee should be given in writing. The investigator should submit the written approval to AstraZeneca before enrolment of any patient into the study. If applicable this approval should clearly state that the exploratory biomarker and pharmacogenetic research is approved. In Japan, the Head of the study site should submit a notification of direction/determination as well as a copy of the Institutional Review Board (IRB) written approval to AstraZeneca. A valid contract between the study site and AstraZeneca Japan should be signed before the investigator can enrol any patient into the study.

The Ethics Committee should approve all advertising used to recruit patients for the study.

AstraZeneca should approve any modifications to the Informed Consent Form that are needed to meet local requirements.

If required by local regulations, the protocol should be re-approved by the Ethics Committee annually.

In Japan, the protocol should be re-approved by the IRB annually. The Principal Investigator should submit progress reports to the IRB via the Head of the study site at the time of the protocol re-approval.

Before enrolment of any patient into the study, the final Clinical Study Protocol, including the final version of the Informed Consent Form, is approved by the national regulatory authority or a notification to the national regulatory authority is done, according to local regulations.

AstraZeneca will handle the distribution of any of these documents to the national regulatory authorities.

AstraZeneca will provide Regulatory Authorities, Ethics Committees and Principal Investigators with safety updates/reports according to local requirements, including SUSARs (Suspected Unexpected Serious Adverse Reactions), where relevant.

Each Principal Investigator is responsible for providing the Ethics Committees/Institutional Review Board (IRB) with reports of any serious and unexpected adverse drug reactions from any other study conducted with the investigational product. AstraZeneca will provide this information to the Principal Investigator so that he/she can meet these reporting requirements.

